6.6.1 Adverse Events

6.6.1.1 Definitions of Adverse Events

The investigator is responsible for reporting all AEs that are observed or reported during the study, regardless of their relationship to study drug or their clinical significance.

An AE is defined as any untoward medical occurrence in a subject enrolled into this study regardless of its causal relationship to study drug. Subjects will be instructed to contact the investigator at any time after randomization if any symptoms develop.

A TEAE is defined as any event not present before exposure to study drug or any event already present that worsens in either intensity or frequency after exposure to study drug.

6.6.1.2 Serious Adverse Events

An SAE is defined as any event that meets one of the following criteria:

- Results in death
- Is immediately life threatening
- Requires inpatient hospitalization or prolongation of existing hospitalization
- Results in persistent or significant disability/incapacity not consistent with baseline level
- Is a congenital anomaly/birth defect

Important medical events that may not result in death, be life threatening, or require hospitalization may be considered SAEs when, based upon appropriate medical judgment, they may jeopardize the subject or may require medical or surgical intervention to prevent one of the outcomes listed in this definition. Examples of such medical events include allergic bronchospasm requiring intensive treatment in an emergency room or at home, blood dyscrasias or convulsions that do not result in inpatient hospitalization, or the development of drug dependency or drug abuse.

6.6.1.3 Eliciting and Documenting Adverse Events

Adverse events will be assessed beginning at enrollment (date of signed informed consent) and up to 30 days after the last dose of study drug, and must be followed until resolution or for 30 days after the subject's last study drug dose, whichever comes first.

Serious AEs that occur more than 30 days after the last dose of study drug need not be reported unless the investigator considers them related to study drug.

At every clinic visit after informed consent and at all phone visits (Table 6-1), subjects will be asked a standard nonleading question to elicit any medically related changes in their well-being. They will also be asked if they have been hospitalized, had any accidents, used any new medications, or changed concomitant medication regimens (both prescription and over-the-counter medications).

In addition to subject observations, AEs identified from any study data (eg, laboratory values, physical examination findings) or identified from the review of other documents (eg, subject diaries) that are relevant to subject safety or considered to be clinically significant, in the medical and scientific judgment of the investigator, will be documented on the AE page in the eCRF.

6.6.1.4 Reporting Adverse Events

All AEs reported or observed during the study will be recorded on the AE page in the eCRF. Information to be collected includes the following:

- Drug treatment
- Dose

- Event term (diagnosis, not symptoms)
- Time of onset
- Investigator-specified assessment of severity and relationship to study drug
- Time of resolution of the event
- Seriousness
- Any required treatment or evaluations
- Outcome

Adverse events resulting from concurrent illnesses, reactions to concurrent illnesses, reactions to concurrent medications, or progression of disease states must also be reported. All AEs will be followed to adequate resolution. The Medical Dictionary for Regulatory Activities (MedDRA) will be used to code all AEs.

Any medical condition that is present at the time that the subject is screened but does not deteriorate should not be reported as an AE. However, if it deteriorates at any time during the study, it should be recorded as an AE.

6.6.1.5 Reporting Serious Adverse Events

Investigators and other study center staff must immediately (ie, within 1 business day) inform [REDACTED] upon learning of any SAE that occurs (whether or not attributable to the study drug). It is the investigator's responsibility to ensure that SAE reporting procedures are followed appropriately. All SAE reports must be faxed to the following number.

- [REDACTED]

Any AE that meets SAE criteria (Section 6.6.1.2) must be entered into the EDC system immediately (ie, within 1 business day) after site personnel first learn about the event. Once the qualifying SAE data are entered, [REDACTED] will be notified by an email alert, which will contain high-level safety information. Additional safety information will be obtained from the EDC system via applicable eCRF pages. If the EDC system is not available, the site should send a completed, manual, paper SAE report form to [REDACTED] by fax:

- [REDACTED]

When the EDC system is again available, the site must enter all applicable information into the EDC system. All supporting source information concerning the SAE (eg, hospital records) should be provided by fax.

If there is a question concerning an SAE, the site needs guidance regarding the reporting of an SAE, the site is returning a call from a Sciformix safety specialist, or the site urgently needs to report an SAE or make [REDACTED] aware of an SAE, the safety hotline should be used:

- [REDACTED]

If a site makes an initial report of an SAE by the safety hotline, the site must subsequently enter all applicable information into the EDC system immediately thereafter.

All SAEs must be reported starting from the time that informed consent for study participation is provided. If the investigator becomes aware of an SAE within 30 days after the subject's last dose of study drug or within 30 days after the last study visit, the SAE must be reported. Serious AEs must be followed until the event resolves, the event or sequelae stabilize, or it is unlikely that additional information can be obtained after demonstration of due diligence with follow-up efforts (ie, the subject or health care practitioner is unable to provide additional information or the subject is lost to follow-up). Serious AEs that occur more than 30 days after the last dose of study drug do not need to be reported unless the investigator considers them related to study drug.

6.6.1.6 Suspected Unexpected Serious Adverse Reactions

The sponsor will promptly evaluate all suspected unexpected serious adverse reactions (SUSARs) and nonserious AEs of special interest against cumulative product experience to identify and expeditiously communicate possible new safety findings to investigators, IRBs, and applicable health authorities, based on applicable legislation.

To determine the reporting requirements for single AE cases, the sponsor will assess the expectedness of these events using the gaboxadol investigator's brochure [REDACTED]

The sponsor will compare the severity of each suspected unexpected serious adverse reaction and the cumulative event frequency reported for the study with the severity and frequency reported in the investigator's brochure.

Reporting requirements will also be based on the investigator's assessment of causality and seriousness, with allowance for upgrading by the sponsor as needed.

6.6.1.7 Assessment of Severity

The severity, or intensity, of an AE refers to the extent to which an AE affects the subject's daily activities. The intensity of the AE will be rated as mild, moderate, or severe using the following criteria:

Mild: An AE that is transient in nature and generally does not interfere with the subject's normal activities.

Moderate: An AE that is sufficiently discomforting to interfere with the subject's normal activities.

Severe: An AE that is incapacitating and prevents normal activities.

Changes in the severity of an AE should be documented to allow an assessment of the duration of the event at each level of intensity to be performed. Adverse events characterized as intermittent do not require documentation of the onset and duration of each episode.

6.6.1.8 Assessment of Causality

The investigator's assessment of an AE's relationship to study drug is part of the documentation process, but it is not a factor in determining what is or is not reported in the study. If there is any doubt as to whether a clinical observation is an AE, the event should be reported.

The relationship or association of the test article in causing or contributing to the AE will be characterized using the following classification and criteria:

Unrelated: This relationship suggests that there is no association between the study drug and the reported event.

Possible: This relationship suggests that treatment with the study drug caused or contributed to the AE, ie, the event follows a reasonable temporal sequence from the time of drug administration or follows a known response pattern to the study drug but could also have been produced by other factors.

Probable: This relationship suggests that a reasonable temporal sequence of the event with drug administration exists and, based upon the known pharmacological action of the drug, known or previously reported adverse reactions to the drug or class of drugs, or judgment based on the investigator's clinical experience, the association of the event with the study drug seems likely. The event disappears or decreases on cessation or reduction of the dose of study drug.

Definite: This relationship suggests that a definite causal relationship exists between drug administration and the AE, and other conditions (concurrent illness, progression/expression of disease state, or concurrent medication reaction) do not appear to explain the event. The event reappears or worsens if the study drug is re-administered.

6.6.1.9 Follow-up of Subjects Reporting Adverse Events

All AEs must be reported in detail on the appropriate page in the eCRF and followed to satisfactory resolution, until the investigator deems the event to be chronic or not clinically significant or until the subject is considered to be stable.

6.6.2 Other Safety Assessments

Safety assessments other than AEs (Section 6.6.1) will include standardized clinical assessment of suicidality (Section 6.8), clinical laboratory evaluations (Section 6.9), and vital sign measurements.

6.6.2.1 Vital Sign Measurements

Vital sign measurements will include weight, blood pressure, heart rate, and temperature. Measurements of blood pressure, heart rate, and temperature should be attempted after the subject has been resting in a supine or sitting position for at least 10 minutes.

6.7 Monitoring Committees

An Internal Monitoring Committee and Scientific Oversight Committee agreement charter will document the roles, responsibilities, scope of activities, communication pathway, and time of meetings.

6.7.1 Internal Monitoring Committee

The Internal Monitoring Committee is a committee that will review unblinded safety and efficacy data when 30 evaluable subjects have completed the EOT visit. It will consist of responsible representatives from Ovid clinical science, clinical pharmacology, statistics, drug safety, and statistical programming.

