After random assignment at Baseline, subjects will receive the assigned package of blinded study treatment according to the treatment code for the first 6 weeks of treatment and will take their first dose of study drug at the clinic. They will receive another assigned package of study treatment at the Week 6 clinic visit.

Each subject (assisted by a legally acceptable representative [LAR]/caregiver) will complete paper sleep diaries and wear actigraphs over the 7-day periods immediately preceding Baseline and the Week 2, Week 6, EOT, and EOS clinic visits. The Baseline, Week 2, Week 6, and EOT visits will be full-day clinic visits.

For each subject, after informed consent is obtained, the maximum duration of individual subject participation will be 21 weeks. A subject will have completed the study when he completes the EOS visit. The end of the study is defined as the date when the last subject completes his last visit (includes follow-up visit).

Safety information will be collected during phone calls at the end of Weeks 1, 4, 8, and 10 (on Days 8, 29, 57, and 71, respectively), in addition to during every clinic visit (screening, baseline, Week 2, Week 6, EOT, and EOS). At the investigator's discretion, subjects may be evaluated at unscheduled clinic visits for reasons related to subject safety. At unscheduled visits, subjects will be queried about AEs, changes in concomitant medications, and suicidality, and safety laboratory assessments may be conducted. Periodic interim blinded

review of safety data will be performed as part of routine pharmacovigilance activities. No interim statistical analysis is planned.

Activities during each period of the study are described by study visit in Section 6.1 and are presented in greater detail in the workbooks for caregiver/clinician/subject assessments.

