5.6 Blinding

The study will be performed in a double-blind manner, with the subjects, LAR/caregivers, investigators, study personnel, monitors, and study sponsor blinded to the identity of all study drug. All study drug will be supplied in identical packaging and will be similar in color, smell, taste, and appearance to enable double-blind conditions.

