5.6.1 Breaking the Blind

A subject's treatment assignment will not be broken until after the last subject has completed the study and the database has been locked, unless medical treatment of the subject depends on knowing the study treatment the subject received. In the event that the blind needs to be broken because of a medical emergency, the investigator may unblind an individual subject's treatment allocation. Before unblinding a subject's treatment assignment and as soon as

possible, the investigator should make every effort to contact the medical monitor to discuss the medical emergency and the reason for revealing the treatment received by that subject. The treatment assignment will be unblinded through the IWRS. Reasons for treatment unblinding must be clearly explained and justified in the eCRF. The date on which the code was broken and the identity of the person responsible must also be documented. If a subject's treatment is unblinded, the sponsor must be notified immediately.

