6.1.7 End-of-Study Visit

[REDACTED] The EOS visit will be scheduled to be completed within 4 to 6 weeks after the subject completes the EOT study visit, any time between the ends of Week 16 and Week 18. For subjects for whom study drug administration is stopped early and an early EOT visit occurred, an EOS visit should be completed within 4 to 6 weeks after completing the early EOT study visit.

The subject's LAR/caregiver will bring the subject's sleep diary and actigraph (issued at the EOT clinic visit), and study staff will manage the sleep diary and actigraph during the visit as detailed in Section 6.1.7.1.

The following schedule of activities should be observed for subjects at the EOS clinic visit:

- Study staff conduct the following assessments that involve subject participation, in the following order: KiTAP and RBANS.

The LAR/caregiver questionnaires and investigator/study staff queries of the LAR/caregiver concerning AEs, concomitant medications, and subject suicidality (Section 6.8) can be completed at any time during the visit.

Details of the order of activities and instructions for assessments at the EOS clinic visit are provided in the workbooks for caregiver/clinician/subject assessments.

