7.8.7 Interim Analyses

No interim statistical analysis will be performed. Periodic interim blinded review of safety data will be performed as part of routine pharmacovigilance activities.

8 Data Quality Assurance

This study will be conducted according to the risk and quality processes described in the relevant procedural documents. The quality management approach to be implemented in this study will be documented and will comply with International Council for Harmonisation (ICH) E6(R2) guidance on quality and risk management.

Standard operating procedures are available for all activities relevant to the quality of this study. Designated personnel will be responsible for implementing and maintaining quality assurance and quality control systems to ensure that the study is conducted and that data are generated, documented, and reported in compliance with the study protocol, Good Clinical Practice (GCP), and Good Laboratory Practice requirements as well as applicable regulatory requirements and local laws, rules, and regulations relating to the conduct of the clinical trial.

At any time, quality assurance representatives of the sponsor and/or regulatory bodies may visit the unit to carry out an audit of the study in compliance with regulatory guidelines and sponsor policy. Such audits will require access to study records, documentation, and regulatory files. At all times, subject privacy will be of utmost importance and will be respected. Typically, sufficient notice will be given to the investigator to prepare for the visit.

In the event of an audit or inspection, the investigator (and institution) must agree to grant the auditor(s) and inspector(s) direct access to all relevant documents and to allocate their time and the time of their staff to discuss any findings or relevant issues. The investigator must notify the sponsor of any regulatory authority inspections and forward copies of the inspection report to the sponsor.

Electronic data systems will be in accordance with applicable aspects of US Title 21 Code of Federal Regulations (CFR) Part 11, ICH Guidelines, GCP, local laws and legislation, and the Health Insurance Portability and Accountability Act.

Responsibility for the accuracy, completeness, and reliability of the study data presented to the sponsor lies with the investigator generating the data.

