10. INTERIM ANALYSIS

No interim statistical analysis will be performed. Periodic interim blinded review of safety data will be performed as part of routine pharmacovigilance activities.

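### Sponsor staff are to review unblinded efficacy and safety data at the 30th evaluable end-of-treatment visit, before the blinding rules allow it, and no interim-analysis section mentions the review

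*Protocol*

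**What the plan says.** **The review.** Protocol 6.7.1 sets the content and the trigger: "The Internal Monitoring Committee is a committee that will review unblinded safety and efficacy data when 30 evaluable subjects have completed the EOT visit". It also sets the membership: "It will consist of responsible representatives from Ovid clinical science, clinical pharmacology, statistics, drug safety, and statistical programming". Protocol 6.7 leaves roles, scope, communication and meeting times to a charter, which is not among the documents.

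**The blinding rules.**
- Protocol 5.6.1: "A subject's treatment assignment will not be broken until after the last subject has completed the study and the database has been locked". The one exception is a subject whose medical treatment depends on knowing the assignment.
- Protocol 5.6 lists among those kept blind the "monitors, and study sponsor blinded to the identity of all study drug". SAP 4.3 repeats this. Neither makes an exception for a committee, and SAP 4.3 sets no lock condition.

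**The interim-analysis sections.** Protocol 3.1 says "No interim statistical analysis is planned", and SAP 3.1 says the same. SAP 10 says "No interim statistical analysis will be performed", as does Protocol 7.8.7. The only ongoing review described in these sections is blinded: "Periodic interim blinded review of safety data will be performed as part of routine pharmacovigilance activities". The SAP text does not mention the Internal Monitoring Committee.

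**When a subject is finished.** Protocol 3.1 counts a subject as complete at the end-of-study (EOS) visit, not at end of treatment (EOT). Protocol 6.1.7 gives the gap: "The EOS visit will be scheduled to be completed within 4 to 6 weeks after the subject completes the EOT study visit".

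**The concern.** A study team that carries out 6.7.1 at its stated trigger breaks 5.6.1. Sponsor functions that take part in analysis and data handling would know assignments while visits, adverse event collection and data cleaning are still open.

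The second issue is the order of events. SAP 1 requires the SAP to be final before the database is locked for the primary analysis. It says nothing about this review. Several efficacy rules appear only in the SAP:
- the exclusion of subjects with a baseline ABC-C total of 16 or less (SAP 8.1.1, with a sensitivity analysis in all subjects);
- the exclusion of subjects with an inconsistent Conners 3 response style at screening (SAP 8.1.4);
- the exact tests of CGI-I response between arms (SAP 8.1.6).

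SAP 12 lists one departure from the protocol, the significance level for the age effect, and none of these three. From the text, a reader cannot tell whether they were fixed before sponsor statisticians could see efficacy by arm.

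**Working it through.** This is a conflict of text. The arithmetic only shows how far the trigger precedes the permitted point.

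**1. The plan's own figures.** Protocol 7.5 plans about 36 enrolled for 30 evaluable completers, an implied loss of 1 − 30/36 = 16.7%. The trigger of 30 is also the N behind the precision table. The Wilson half-width is z·√[p(1−p)/n + z²/(4n²)] / (1 + z²/n). With p = 0.20, n = 30 and z = 1.96 this is 1.96 × √(0.005333 + 0.001067) / 1.128 = 13.9%, which agrees with Table 7-1. The review is therefore set at the full planned evaluable sample.

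**2. The conditions side by side.**

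| Condition for unblinding in Protocol 5.6.1 | State at the 6.7.1 trigger |
|---|---|
| Last subject has completed the study (EOS) | Normally not met: the 30th subject has only just reached EOT |
| Database locked | Not met: 6.7.1 does not mention lock |
| Or: a subject's medical treatment requires it | Not the purpose of the review |

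Even if no EOS visit were pending, the lock condition would remain.

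**3. Time from EOT to EOS (Protocol Table 6-1).** EOT is Day 85 and EOS is Day 113 with a window of +14 days. The gap is 113 − 85 = 28 days to 127 − 85 = 42 days.

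**4. Subjects not yet at EOT.** If 36 are enrolled, 30/36 = 83.3% have reached EOT as evaluable. The number still to come is 36 − 30 − losses:
- 6 lost (the planned 16.7%): 0 to come;
- 10% lost (assumed): 32.4 − 30 = about 2;
- 5% lost (assumed): 34.2 − 30 = about 4;
- none lost: 6 to come, and 6/36 = 16.7%.

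**5. Completers still awaiting EOS.** The accrual rate is not given. Assume the 30 EOT visits are spread evenly over 6 to 18 months (183 to 548 days):
- fewest: 30 × 28/548 = 1.5;
- most: 30 × 42/183 = 6.9.

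That is about 2 to 7 subjects.

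**6. What is still open.** For subjects past EOT, it is mainly off-drug safety follow-up, since the named efficacy analyses are at Weeks 2, 6 and 12. That follow-up still matters. The last dose is taken at the EOT visit (Protocol 3.1.1), adverse events are collected for 30 days afterwards (Protocol 6.6.1.3), and SAP 9.1.1 counts events in that window as treatment-emergent, which makes them primary endpoint data. For any subject not yet at EOT, on-treatment data are open as well.

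**The case against.** - **A descriptive look is not an interim statistical analysis.** Protocol 6.7.1 names no test, stopping rule or decision, so the statements that no interim analysis will be done may be literally true. This stands as far as it goes. The review still breaks 5.6.1, and the interim sections still omit an unblinded look at efficacy.
- **The word *when* may mean once, at any later time, and the charter may set the meeting after lock.** This reading is possible, but it leaves the stated trigger without a purpose, and 6.7.1 defers nothing to last EOS or to lock. A charter can restrict who sees what. It cannot amend 5.6.1.
- **The sponsor-blinded statements in 5.6 and SAP 4.3 have no time limit, so only 5.6.1 fixes the timing.** Fair. The sharp conflict is with 5.6.1; the other two sections add that no committee exception exists.
- **Rules found only in the SAP are expected.** Protocol 7.8 leaves detailed methods to the SAP and lets it modify the plan. Protocol 6.3.1.4 already collects the Conners long form to check reporter reliability, CGI-I is already a secondary endpoint, and Protocol 7.8.5 calls its modelling post hoc. This stands, and it reduces what there is to protect. These rules show why the order of events matters, not that anything was done wrongly.
- **The counts are soft.** Thirty-six is an estimate, *evaluable* is not defined in either analysis-set section, and early discontinuers also have EOT and EOS visits. This stands. The conflict does not depend on the counts.
- **The stakes are low.** There is no confirmatory test, all arms are active, and external experts separately monitor safety (Protocol 6.7.2). This stands, and it limits the severity.

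**Conclusion.** The concern holds. Carried out at its stated trigger, 6.7.1 breaks the blind that 5.6.1 maintains, whatever the loss rate, because the database is not locked and at least the 30th subject normally has EOS 28 to 42 days ahead. The 0 to 6 subjects short of EOT assumes exactly 36 enrolled. The 2 to 7 completers awaiting EOS assumes even accrual over 6 to 18 months.

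The text permits the SAP to be finalised after the review but does not show that it was. Signature pages are not in the public copies, so a sign-off date may exist that settles this. No type I error rate or sample size changes: SAP 11.1 treats all p-values as exploratory and the primary endpoints are descriptive. The exposure is operational bias in SAP rules, evaluability calls and deviation decisions. Nothing in 6.7.1 unblinds caregivers, investigators or raters. This should be fixed; it does not undermine the trial. Confidence in the contradiction is high.

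**What to change.** Choose one of two routes.

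1. **Move the review.** Change the trigger in Protocol 6.7.1 to after the last subject's last visit and database lock. No other section then needs to change.
2. **Keep the review and declare it.**
   - Describe it as an unblinded interim review in Protocol 3.1, 5.6, 5.6.1 and 7.8.7 and in SAP 3.1, 4.3 and 10. Give its purpose and name the roles that are unblinded.
   - Sign and date the SAP before any unblinded data are released.
   - State in the protocol or the charter that unblinded members take no part in SAP edits, evaluability decisions or deviation decisions until lock.

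The first route costs a delay of some weeks to the review. The second costs wording in both documents, a SAP sign-off date, and the loss of the unblinded members from data decisions until lock.
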